#### Experimental Design and Methods

*Participants:* TBI subjects enrolled in Aim 1.1 will be entered into a data registry with comprehensive contact information, including contact information (phone, email, fax, mail address) not just on participants, but also on multiple collaterals we can contact for 6 month and 1 year assessments.

*Assessments:* Initial screening will be done prior to tDCS intervention, and will be performed verbally to resemble subsequent phone interviews. These assessments will include the Neurobehavioral Symptom Inventory (NSI), and the PROMIS-29 quality of life profile. Dimensions queried by the PROMIS-29 survey will include physical function, anxiety, depression, fatigue, pain, sleep, and social roles. At 6 months and 1 year after the end of stimulation, subjects will be contacted by phone by the research team for a brief assessment of their post-traumatic symptoms and quality of life. Subjects not able to be contacted by phone will be sent a letter with the surveys in paper form to be returned via mail, fax, or email.

Specific Aim 1.3: Clinical predictors of tDCS response

#### Experimental Design and Methods

*Participants:* TBI subjects from Aim 1.1 will be carried forward for study in Aim 1.3. Key clinical variables in the study group will be analyzed for association with tDCS effect, namely, lesser post-traumatic symptom burden as measured by the NSI, mild versus moderate severity of TBI, lack of neuroimaging abnormalities on MRI, and higher premorbid level of intelligence as measured by the WTAR, as these are factors shown to predict better recovery from TBI.

Specific Aim 2.1: Effectiveness of tDCS for depression after mmTBI

## PROTOCOL TITLE: Transcranial direct current stimulation for treatment of deficits after traumatic brain injury.

We will undertake an investigation of tDCS for depressed mood after mmTBI. The same protocol as for Aim 1 will be employed to investigate Aim 2, with a focus on depressive symptoms. The stimulation paradigm is similar to the regimen used by Brunoni et al. in their study comparing tDCS to sertraline for depression (10 sessions, 30 minutes/session). However, their paradigm is limited in its power to identify the therapeutic element of tDCS for depression, because it does not separate the effects of simultaneous anodal/cathodal influences. Our configuration with the cathode placed on the contralateral arm, developed and tested in our lab, thereby ensures that only one type of neuromodulation is delivered to the brain, rather than two. Subjects receiving active anodal left prefrontal tDCS for ten days will experience significantly greater improvement in depressive symptoms compared to sham stimulation, as assessed with NIH Common Data Elements depression instruments, that will be detectable immediately after stimulation and at 1 month post-stimulation.

### Experimental Design and Methods

**Recruitment:** Recruitment, enrollment, and data collection for Aim 2 will be identical to the experimental design of Aim 1. Subjects will be randomly assigned to active stimulation or sham stimulation groups.

**Depression Assessments:** As part of the neuropsychological test battery administered to the participants before, immediately after, and at 1 month after tDCS, subjects will be assessed for depressive symptoms using NIH Common Data Elements instruments as well as reliable and valid instruments for detecting mood disturbances in TBI populations. These tests are the Beck Depression Inventory (BDI-II), and the Hamilton Rating Scale for Depression (HAM-D). Post-traumatic stress disorder (PTSD) symptoms, which often predispose to depression after TBI, will be assessed using the PTSD Checklist (PCL). These will be conducted verbally, so as to ensure similarity of delivery with the long-term assessments. Any patient who reports thoughts of death or suicidal ideation at any point during the stimulation protocol or assessments will be immediately evaluated by the PI and given appropriate emergency medical care at the UNM Psychiatric Emergency Service.

**Stimulation Protocol:** The protocol will be identical to the stimulation regimen described in Aim 1. During the procedure for each stimulation session, participants will be asked to rate their mood according to a 10-point visual analog scale before and after each stimulation session (10 sessions total). This will monitor for daily fluctuations in mood as well as any rare stimulation-related severe mood changes.

### Specific Aim 2.2:

The subjects from Aim 2.1 will be automatically included. At 6 months and 1 year after stimulation, subjects will be contacted via telephone and administered the depression assessment tools utilized before, immediately after, and 1 month after stimulation.

**Specific Aim 2.3:** Subjects from Aim 2.1 will be carried forward for study in Aim 2.3. Patient and injury characteristics will predict positive response to tDCS, namely, higher premorbid intellectual function (WTAR), lesser severity of injury (mild versus moderate), lack of neuroimaging abnormalities on MRI, and more severe pre-stimulation depressive symptoms (BDI, HAM-D). Understanding which of the clinical variables described above moderate the efficacy of tDCS in mmTBI will allow for more precise patient selection and better overall efficacy in future applications.

Each of the 80 participants will receive \$20/hr in the form of cash cards for taking part in the study.. This is felt to be a fair amount that is not coercive and will help decrease attrition for this study which involves many visits.

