### Specific Aim 2: tDCS for depressive symptoms in mmTBI

Experiments in this aim will test the hypothesis that left prefrontal anodal tDCS in patients with mmTBI will significantly reduce depressive symptoms compared to sham stimulation. Aim 2.1: Patients will be assessed for symptoms of depression via self-report instruments and clinician-administered scales from NIH Common Data Elements before, immediately after, and one month after the stimulation protocol. Aim 2.2: Persistence of antidepressant benefit will be assessed via telephone interview at 6 months and one year. Aim 2.3: clinical predictors of tDCS response such as EEG frontal theta synchrony, injury severity, premorbid intelligence, neuroimaging abnormalities, and symptom burden will be determined.

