## 5. Study Endpoints

Primary endpoint: change in scores on the EXAMINER battery from before to after stimulation.

Secondary endpoints: change in score on the Neurobehavioral Symptom Inventory, Beck Depression Inventory-II, Hamilton Rating Scale for Depression, change in frontal midline theta synchrony on EEG, change in MRI abnormalities, and quality of life measure from time 0 to 1 year.

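### Aim 2.3 names baseline BDI-II/HAM-D as a predictor of response measured by change on the same scales, and writes no arm-by-baseline test to separate a tDCS effect from regression to the mean

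*Combined protocol and SAP*

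**What the plan says.** Section 10, Specific Aim 2.3, states its hypothesis as "Patient and injury characteristics will predict positive response to tDCS". It lists higher WTAR, milder injury, no MRI abnormality and "more severe pre-stimulation depressive symptoms (BDI, HAM-D". It gives the purpose as "Understanding which of the clinical variables described above moderate the efficacy of tDCS in mmTBI", and says that this "will allow for more precise patient selection and better overall efficacy in future applications".

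Section 5 lists among the secondary endpoints "change in score on the Neurobehavioral Symptom Inventory, Beck Depression Inventory-II, Hamilton Rating Scale for Depression". Under Aim 2.1 in section 10, "before, immediately after, and at 1 month after tDCS, subjects will be assessed for depressive symptoms", and "Subjects will be randomly assigned to active stimulation or sham stimulation groups".

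On method, section 1 (Specific Aim 2) says only "clinical predictors of tDCS response such as EEG frontal theta synchrony, injury severity, premorbid intelligence, neuroimaging abnormalities, and symptom burden will be determined". Section 11, repeated in section 14, writes mixed models for the Examiner composites, the NSI cognitive items and PROMIS-29. It enters severity, WTAR and NSI as covariates, and says that this identifies predictors of treatment response through contrasts that it does not spell out. No covariate-by-arm term is named, BDI-II and HAM-D are not among the covariates, and neither scale has a model.

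**The concern.** Baseline BDI-II or HAM-D is the predictor, and it is also one of the two terms in the change score. Under imperfect retest correlation, patients who score high before stimulation tend to score lower afterwards, and patients who score low tend to drift up. The hypothesised direction is the one that this produces without any treatment effect. It comes from the shared baseline term and not from selection, since section 4 sets no depression threshold for entry.

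Sham patients regress in the same way, so the comparison of arms is what removes the artefact, and the plan does not write that comparison down. Its wording elsewhere leans towards analyses without it: section 2 plans to correlate response with EEG measures in order to find likely beneficiaries, and section 11 treats a covariate effect as a predictor of response.

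Aim 2.3 is meant to inform later patient selection. A finding that more depressed patients respond better could reach that use while reflecting only measurement noise.

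**Working it through.** **The plan's own figure.** The documents give none for Aim 2.3. The nearest is 80% power for 40 versus 40 at d = 0.7. The noncentrality is 0.7 × √20 = 3.13, which gives 87.1% by the exact t-test at two-sided 0.05, and 79.9% at two-sided 0.025. No alpha is stated. This mismatch is separate and does not bear on the present point.

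**Inputs.** From section 11: 40 active and 40 sham TBI patients. Assumed: two-sided 0.05, no tDCS effect, equal SDs at both visits, normal scores, no dropout. The baseline-to-post correlation r is not in the documents and is taken as 0.5 to 0.9.

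**Formula.** Let X be the baseline and Y the post score, both with SD 1, and let improvement be X − Y.

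- Cov(X, X − Y) = 1 − r
- Var(X − Y) = 2(1 − r)
- Corr(X, X − Y) = (1 − r)/√(2(1 − r)) = √((1 − r)/2)

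At r = 0.7 this is √0.15 = 0.387.

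**Chance of significance in the predicted direction, no tDCS effect.** By Fisher's z it is about Φ(atanh(corr) × √(n − 3) − 1.96). At r = 0.7 and n = 40: 0.4085 × 6.083 − 1.96 = 0.525, and Φ(0.525) = 0.70. Simulation with 20,000 trials per value of r gives:

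| r | Corr. of baseline with improvement | Active arm alone, n = 40 | Both arms pooled, adjusted for arm, n = 80 | Arm-by-baseline, two-sided |
|---|---|---|---|---|
| 0.5 | 0.50 | 92.6% | 99.8% | 5.0% |
| 0.6 | 0.45 | 84.7% | 98.8% | 4.8% |
| 0.7 | 0.39 | 70.9% | 94.9% | 4.9% |
| 0.8 | 0.32 | 52.3% | 82.0% | 5.2% |
| 0.9 | 0.22 | 28.7% | 51.0% | 5.1% |

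A separate run of 4,000 trials per cell gave 92% to 29% at n = 40 and 99.8% to 50% at n = 80. In the predicted direction alone, the arm-by-baseline test rejects in 2.4% to 2.7%. That is the like-for-like comparison with the third and fourth columns.

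**Why the interaction is safe.** The slope of improvement on baseline is one minus the slope of post score on baseline. Regression to the mean is the same in both arms, so it cancels in the difference between slopes, whether the outcome is the post score or the change.

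**Sensitivity at n = 40.**
- The rate falls below 50% from r of about 0.81 (about 0.91 at n = 80).
- On a skewed, zero-bounded scale (assumed shape) the rates are 87%, 67%, 54% and 37% at r = 0.5, 0.7, 0.8 and 0.9.
- On a scale floored at zero (assumed mean 14, SD 11 before flooring), the range over the same r is 94% to 27%, with the interaction test at 4% to 5%.
- If either scale may confirm the hypothesis (assumed cross-scale correlation 0.7), the rates are 98%, 85%, 69% and 43% at r = 0.5, 0.7, 0.8 and 0.9.

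**The case against.** The strongest reply is that this criticises an analysis that the plan does not contain. Aim 2.3 gives a hypothesis and no test. Its purpose is put in terms of moderating efficacy, which is a question about the active-sham difference, and there is a randomised sham arm to answer it. The valid contrast is therefore possible and may be what was intended. The nearest written model is also not a baseline-versus-change correlation: in a model of scores over visits, the main effect of baseline depression would point to higher scores, not to improvement. Regression to the mean enters only through a baseline-by-time contrast without arm, or through change analysed within one arm or pooled.

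Most of this stands. A reader might infer that the trial as written would usually confirm the hypothesis whether or not tDCS works. The documents do not support that: the artefact depends on an analysis that they leave open, and its frequency depends on a retest correlation that they do not give. At r = 0.9 with 40 patients it is 29%. A reader might also infer that only the baseline depression predictor is affected. The shared-term artefact is indeed specific to it, but without a predictor-by-arm test, WTAR, injury severity and MRI findings would also be shown only to be prognostic.

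What the reply does not remove is the gap. An intention to study moderation is not a specified test, and the one predictor method that the plan states has no arm interaction.

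**Conclusion.** The concern holds in a conditional form. Aim 2.3 pairs a predictor with change on its own scale, defines no response, and has no written test that could answer its own question. If baseline severity is related to change within the active arm or pooled over arms, a treatment with no effect would favour the hypothesis far more often than the nominal 2.5% in that direction: about 93% to 29% with 40 patients and about 99.8% to 51% with 80, for r from 0.5 to 0.9. The arm-by-baseline test holds its level throughout. These figures rest on the assumed range of r, equal SDs at the two visits and two-sided 0.05. The flooring and skewness checks change the percentages but not the conclusion.

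This is a secondary, predictor-seeking aim. It does not touch the randomised comparison of depression scores or the primary endpoint. It should be corrected because the result is meant to guide patient selection and the repair uses data already planned.

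**What to change.** In section 10 (Aim 2.3) and section 11:

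1. Keep baseline BDI-II and HAM-D as candidate moderators. For each scale, model the post-stimulation score on arm, baseline score and arm-by-baseline at a named visit (immediate or 1 month), or use arm-by-baseline-by-time in the mixed model. State that response means the active-sham difference in that score.
2. Claim that baseline severity predicts response to tDCS only if the active and sham slopes differ. Draw no inference from baseline-versus-change associations within an arm or pooled, or from responder rates by baseline severity.
3. Use the same predictor-by-arm test for WTAR, injury severity and MRI findings.

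The cost is a paragraph of protocol text and one model per scale and predictor, with no new data. The real price is power. With 40 per arm and both variables in SD units, the standard error of the slope difference is about √(1 − r²) × √(2/40). At r = 0.7 that is 0.714 × 0.224 = 0.16, so roughly 80% power needs a slope difference of about 2.8 × 0.16 = 0.45 (0.54 at r = 0.5 and 0.27 at r = 0.9). A positive predictor claim becomes less likely, and a null result should be reported as inconclusive and not as absence of moderation.

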## 1. Objectives

Our long-term goal is to develop safe and effective treatments for symptoms of mild to moderate TBI (mmTBI) that restore patients to higher levels of functioning, decrease disability, and promote brain healing. The objective of this application is to investigate the use of transcranial direct current stimulation (tDCS) to treat symptoms of executive dysfunction and depression in patients with mmTBI. Our central hypotheses are (1) tDCS paired with relevant cognitive training facilitates improves executive function on NIH-approved neuropsychological measures, (2) tDCS reduces depression scores on NIH Common Data Elements for TBI, (3) that these improvements in emotion and cognition will be detectable up to one year after stimulation, (4) (4) certain clinical variables will reliably predict response to tDCS, such as age, education level, injury severity, and magnetic resonance imaging (MRI) evidence of structural/functional/metabolic abnormalities and (5) quantitative electroencephalography (EEG) will demonstrate changes in frontal midline theta band power and theta band synchrony, markers of cognitive control, in responders. These objectives were formulated based on our clinical experience with [name] (project mentor) characterizing symptomatic patients with mmTBI in the post-acute setting, groundbreaking research led by [name] (project mentor) that has demonstrated robust increases in attention and learning with tDCS, and extensive evidence accumulated by co-junior investigator on the grant application [name] on EEG measures of executive dysfunction.

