### Specific Aim 1: tDCS for executive dysfunction in mmTBI

Experiments in this aim will test the hypothesis that in patients with mmTBI, left prefrontal anodal tDCS concurrent with cognitive training for up to ten consecutive weekdays will result in significantly more improvement in executive function compared to sham stimulation. Patients with cognitive complaints 3 months to 15 years after mmTBI will be recruited from local emergency departments and brain injury clinics. Healthy controls will also be recruited through flyers, advertisements and word of mouth. Aim 1.1: tDCS will be paired with computer-based cognitive training tasks of response inhibition, set shifting, and working memory, while executive function will be measured with the NIH Examiner battery before, immediately after, and one month after stimulation. Pre-and post-stimulation EEG and MRI may be obtained. During EEG and MRI participants may be asked to rest quietly or perform simple tasks. Aim 1.2: Persistence of post-traumatic symptom reduction and quality of life improvement will be assessed with Common Data Elements instruments via telephone interview at 6 months and one year. Aim 1.3: Clinical predictors of tDCS response including EEG frontal theta synchrony, injury severity, presence of neuroimaging abnormalities, premorbid intelligence, and post-traumatic symptom burden will be determined with linear mixed-models analysis.

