### Experimental Design and Methods

**Participants:** Eighty TBI subjects will be recruited for this study, all having suffered mild or moderate TBI (mmTBI, as defined before) at least 3 months prior to study enrollment, but not more than 15 years prior to enrollment. 80 age- and sex-matched healthy controls will be recruited. All participants will be 18-55 years of age. We will expect to screen approximately 120 patients with mmTBI in order to reach our goal of 80 TBI subjects. The experimental pre-post, double-blind design is graphically displayed. It includes randomization of TBI patients to either a left-sided active transcranial direct current stimulation (tDCS) protocol, or sham treatment group to foster isolation and identification of any tDCS treatment effects. To enhance our statistical power to identify predictors of treatment response in mmTBI patients, 40 TBI subjects and 40 controls will be assigned to each group: left-sham and left-active.

**Recruitment:** Recruitment primarily will be through the UNM Hospital Emergency Department (ED) (the only Level 1 trauma center in New Mexico). The UNM Health Sciences Center (HSC) Clinical and Translational Science Center (CTSC) Participant Recruitment Service (PRS) for Clinical Research will monitor ED intake records for patients who meet criteria once released from the hospital, then notify the study team of these cases. A second means of recruitment will involve direct referrals from UNM and non-UNM ED physicians and/or referrals from any clinic in the Albuquerque metropolitan area, via the distribution of flyers and calls to clinical directors to publicize the study. A third means of recruitment will involve information listed on the UNM CBRR and MRN websites, and posted flyers.

**PROTOCOL TITLE:** Transcranial direct current stimulation for treatment of deficits after traumatic brain injury.

[figure not shown]

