Statistical analyses will utilize the CTSC Biostatistics core. Power analyses and statistical analysis strategy were determined with our statistician [name], who will continue to provide recommendations and support throughout the project. Sufficient group sizes were determined on the basis of data derived from preliminary studies. Clark and colleagues found an effect size of Cohen's  $d = 1.2$  for tDCS to induce improvements in cognition. For our power calculations we will assume a more conservative effect size of  $d = 0.7$  which is consistent with a recent meta-analysis of tDCS effect sizes. With 40 tDCS treatment patients compared to 40 sham patients and an effect size of 0.7, we have 80% power to detect effects of active versus sham treatment in a two-sample t-test. Power in the linear mixed model analysis should be superior that that of the t-test. For Aim 1.1, the central analyses evaluate group (active vs. sham) differences in the EEG data and on the three Examiner composite variables across the three initial time points (before, immediately after, and 1 month after tDCS stimulation protocol). To test this hypothesis, three separate linear mixed models analyses will be performed using the three Examiner composite scores (Fluency, Cognitive Control, Working Memory) as dependent variables. In each analysis, we will incorporate three covariates that may predict variation in learning (severity: mild vs. moderate, premorbid intelligence: WTAR score, and symptom burden: NSI). This will allow us to determine predictors of treatment response (Specific Aim 1.3). Sex, ethnicity, and age will also be entered into the statistical model. The effects of these covariates will be estimated by constructing appropriate contrasts in model effects. A similar set of analyses will evaluate group differences on the variables assessed in our long-term oral/phone follow-up (five data points: (1) before tDCS, (2) immediately after tDCS, (3) 1 month post-tDCS, (4) 6 months, and (5) 1 year) for Aim 1.2. For these analyses dependent variables will be the total cognitive items score of the NSI and the PROMIS-29 profile total score). Significant effects will be followed up with more fine-grained analysis of the components of composite scores. The use of linear mixed-models minimizes the adverse impact of a missing data point, which may well occur in a longitudinal clinical study such as this. Expected attrition will be taken into account with an intention-to-treat analysis. Missing data patterns will be analyzed to assess the extent to which they are informative (in contrast to missing at random), and analyses adjusted accordingly. All EEG data will undergo standard preprocessing (e.g. motion correction, spatial normalization) and quality control prior to statistical modeling. Depending on the specific question of the study, data may be analyzed using the general linear model, independent components analysis, machine learning techniques, or a variety of other standard approaches for neuroimaging data.

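### Aims 1.3 and 2.3 state predictors of tDCS response in definite terms, but the predictor lists differ within each aim and there is no error control or exploratory label

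*Combined protocol and SAP*

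**What the plan says.** **Status of the question.** Section 1 (Objectives) lists as its fourth central hypothesis that "certain clinical variables will reliably predict response to tDCS, such as age, education level, injury severity" and MRI abnormalities. The Specific Aim 1 paragraph says: "Clinical predictors of tDCS response including EEG frontal theta synchrony, injury severity, presence of neuroimaging abnormalities, premorbid intelligence, and post-traumatic symptom burden will be determined". Section 10 states the direction expected for each predictor under Aim 2.3 and adds: "Understanding which of the clinical variables described above moderate the efficacy of tDCS in mmTBI will allow for more precise patient selection". That sentence goes on to place the benefit in future applications. Section 10 also links the group allocation to this question: "To enhance our statistical power to identify predictors of treatment response in mmTBI patients, 40 TBI subjects and 40 controls will be assigned".

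**Predictors for Aim 1.3.**
- Specific Aim 1 paragraph: five (EEG theta synchrony, severity, imaging abnormality, premorbid intelligence, symptom burden), in an open-ended list.
- Section 10, Specific Aim 1.3: four; EEG is absent.
- Section 11, repeated in section 14: three (severity, WTAR, NSI), with sex, ethnicity and age as further terms, in three separate mixed models, one per EXAMINER composite.

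**Predictors for Aim 2.3.**
- Specific Aim 2 paragraph: the same five, again open-ended.
- Section 10, Specific Aim 2.3: four (WTAR, severity, MRI, baseline depression). Three are shared with the aims text.
- Outcomes: BDI-II and HAM-D. Section 11 describes no analysis for Aim 2.

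**Analysis.** On the covariates, section 11 says: "The effects of these covariates will be estimated by constructing appropriate contrasts in model effects". It states no alpha, order of testing, adjustment or exploratory status for them.

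**The concern.** A hypothesis worded as reliable prediction, with a stated use in selecting patients, needs one of two things: a defined family of tests with an error rate, or a plain statement that it is exploratory. The plan has neither. Because the list changes from section to section and no predictor-outcome pair is designated, whichever pairing crosses the threshold could be reported as the predictor.

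What is at stake is the selection of patients in later work. A chance finding could be carried forward as a moderator. Writing the correct arm-by-predictor term into the models, which section 11 does not clearly do, would not cure this, because the family would still be uncontrolled.

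**Working it through.** **1. The plan's own figure.** Section 11 gives no error rate for the predictor aims. Its only power statement concerns the arms: "we have 80% power to detect effects of active versus sham treatment in a two-sample t-test". The inputs given there are 40 per arm and d = 0.7. A two-sample t-test with these inputs and two-sided 0.05 has 87.1% power. A figure near 80% appears with alpha 0.025 (79.9%) or with 33 per arm (80.0%), and the plan states neither. The stated 80% errs on the cautious side and does not bear on this point. It does show that no power was worked out for a predictor or an interaction.

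**2. Number of tests.** Each predictor-outcome pair is counted once, ignoring repeated time points.
- Section 11 models: 3 predictors × 3 composites = 9.
- Procedures text, section 10: 4 × 3 + 4 × 2 = 20.
- Aims text, section 1: 5 × 3 + 5 × 2 = 25.

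**3. Independent tests.** Assumptions: two-sided 0.05 per test and no true predictors. The chance of at least one false positive is 1 − 0.95^m.
- m = 9: 1 − 0.95^9 = 37.0%; expected false positives 9 × 0.05 = 0.45.
- m = 20: 1 − 0.95^20 = 64.2%; expected 1.00.
- m = 25: 1 − 0.95^25 = 72.3%; expected 1.25.

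**4. Correlated tests.** The plan gives no correlations, so they are assumed. Test statistics were simulated as multivariate normal, with one common correlation among outcomes and one among predictors. The table shows the share of draws in which any |Z| exceeds 1.96.

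| Outcome r, predictor r | 9 tests (3 × 3) | 20 tests (4 × 5) | 25 tests (5 × 5) |
|---|---|---|---|
| 0, 0 | 37% | 64% | 72% |
| 0.5, 0 | 33% | 55% | 64% |
| 0.5, 0.5 | 29% | 48% | 55% |
| 0.7, 0.5 | 26% | 41% | 46% |

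The 4 × 5 column treats the four predictors of each aim as one common set.

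**5. Each aim alone, on the aims-text lists.** Over the same four scenarios, Aim 1.3 (5 × 3) gives 36–54% and Aim 2.3 (5 × 2) gives 29–40%.

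**The case against.** **The larger counts are constructed.** Only nine predictor-by-composite tests can be read from the written models. The 20 and 25 come from crossing lists with outcomes, and every Aim 2.3 test is inferred because no analysis is written. This stands, and it is why a range is given. A reader might infer that a false predictor is more likely than not. The documents do not support that as a general statement: it fails on nine tests, depends on correlation for 20 and 25, and for those counts requires pooling two aims with different outcomes.

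**Direction.** Section 10 predicts the sign of each effect. If a result counted only in the stated direction, the independent-test figures would be 1 − 0.975^9 = 20%, 1 − 0.975^20 = 40% and 1 − 0.975^25 = 47%. The plan does not say that results will be read this way, but the point is fair. Even 20% is four times the nominal 5%.

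**Status.** A reader might infer that the plan promises confirmatory claims, or that this trial would choose who is offered tDCS by predictor. Neither is written. Section 5 lists no predictor endpoint, section 10 speaks of association for Aim 1.3, and the patient-selection sentence concerns future applications. What does stand is that the hypothesis is put in definite terms without an exploratory label.

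**Other gaps are more basic.** Section 11 names no arm-by-predictor term, Aim 2.3 has no model, and EEG and MRI are planned only for subsets. All true, but closing those gaps would not settle how many tests are run or how they are to be read.

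**Conclusion.** The concern holds in this form: Aims 1.3 and 2.3 are worded as definite prediction, with no alpha, hierarchy, multiplicity control or exploratory label, and with predictor lists that disagree within each aim. The chance of at least one false predictor is about 26–37% on the nine tests supported by section 11, about 41–64% on 20 and about 46–72% on 25. These figures rest on an assumed two-sided 0.05, no true predictors, assumed correlations and one test per pair. The defect is present on every count; only its size varies.

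The active-versus-sham comparison is not affected. The change should be made because it governs what the trial may conclude about who responds, but it does not threaten the main result.

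**What to change.** In sections 10 and 11 (and the repeated text in section 14):
- Fix one predictor list and one outcome list per aim, and make section 1 match.
- Label Aims 1.3 and 2.3 exploratory. Report arm-by-predictor estimates with 95% confidence intervals and state how many were tested.
- Reword the fourth hypothesis in section 1 and the patient-selection sentence under Aim 2.3 as hypothesis-generating.
- If a firm predictor claim is wanted, name one predictor-outcome pair per aim in advance and apply Holm or Benjamini-Hochberg to the rest. For scale, a Bonferroni level over all 25 tests would be 0.05/25 = 0.002.

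The cost is wording only, with no extra participants, visits or data. The downside is a weaker claim for any predictor found.
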